## 8.3. Exploratory Immunogenicity Analyses

### 8.3.1. Maternal immunogenicity cofactors for maternal and neonatal anti-PT antibody responses following intrapartum BOOSTRIX

Summaries and analysis of immunogenicity data will be presented for maternal and infant subjects in the BOOSTRIX group for anti-PT antibody responses at time of delivery or birth, as applicable. Serum IgG antibody concentrations to PT will be summarized by maternal age (18-29, 30-39 years old), parity (primiparous vs multiparous), GA at time of vaccination (14-17, 18-21, 22-26 weeks), GA at time of delivery (28-32, 33-36, 37+ weeks), and infant birthweight. Analysis will include GMCs along with corresponding 95% confidence intervals ([Table 37](#), [Table 38](#), [Table 39](#), and [Table 40](#)).

Additionally, regression modelling will be employed to evaluate the association of log-transformed anti-PT antibody response with each of the stratified maternal cofactors defined previously, as well as with infant birthweight as a continuous variable. Separate models will be used for each analysis population and each cofactor. The analysis of variance model for a stratified cofactors is as follows,

$$\ln(titer) = \beta_0 + \beta_{1i}x_i + \varepsilon;$$

where  $\beta_0$  is the intercept,  $x_i$  is a categorical variable with  $i$  levels for a cofactor with  $i + 1$  levels,  $\beta_{1i}$  is the regression coefficient for each level of the covariate  $x_i$ , and  $\varepsilon$  is random error assumed to be normally distributed. The model will be constructed using reference cell coding; a single level of each cofactor will be used as the reference level and the parameter  $\beta_{1i}$  will be estimated for the remaining levels.

The model for the continuous cofactor of infant birthweight is as follows,

$$\ln(titer) = \alpha_0 + \alpha_1z + \varepsilon;$$

where  $\alpha_0$  is the intercept,  $\alpha_1$  is the regression coefficient,  $z$  is the continuous covariate, and  $\varepsilon$  is random error assumed to be normally distributed.

The models will be produced using PROC GLM or equivalent in SAS. All assumptions for regression models will be assessed by viewing diagnostic plots such as residual plots and QQ plots. The sample sizes, parameter estimates, and parameter standard errors will be presented in [Table 41](#), [Table 42](#), [Table 43](#), and [Table 44](#). For the analysis of variance models of categorical cofactors, the ratio of the GMC of each non-reference level with respect to the GMCs of the reference level will be computed and displayed along with the 95% confidence interval. These values are calculated by exponentiating the level-specific parameter estimate  $\hat{\beta}_{1i}$  and its 95% confidence interval.

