7.3. Enrollment/Baseline

Enrollment and Vaccination Visit, Day 1: Clinic Visit, Pregnant Women (Visit 01 or V01)

- Reconfirm subject's willingness to participate prior to performing any study procedures, including administration of the study vaccination.
- Obtain informed consent (if screening and enrollment visits have been combined).
- Review eligibility criteria with subjects prior to the study vaccination to ensure eligibility.
- Complete medical history and any updates obtained by interview and/or review of medical charts of subjects since the screening visit will be reviewed with subjects prior to the study vaccination to ensure eligibility.
- All concomitant medications and vaccinations will be reviewed with subjects prior to the study vaccination for accuracy and completeness. Any new concomitant medications/vaccinations taken since the screening visit will be reviewed with subjects and used in the assessment for eligibility, prior to the study vaccination. Medications reported in the eCRF are limited to those taken within 30 days prior to the study vaccination. Subjects will be reminded they should not plan to receive any live or inactivated vaccine within 30 or 14 days, respectively, after study vaccination.
- Vital signs, namely oral temperature, pulse, and blood pressure, will be obtained prior to the study vaccination. Vital signs assessed on Day 1 prior to the study vaccination will be considered as baseline. Subjects will be asked not to eat or drink anything hot or cold, or smoke within 10 minutes prior to taking an oral temperature.

- Height and weight will be obtained, if not done on screening visit.
- A targeted physical examination may be performed prior to the study vaccination by a study clinician licensed to make medical diagnoses and listed on the Form FDA 1572 as the site principal investigator or sub-investigator, if indicated based on review of complete medical history and any updates obtained by interview of subjects or medical chart review since the screening visit. For pregnant women, an examination performed by her own obstetrical clinician may also provide data when a targeted exam is called for.
- Approximately 30 mL of venous blood will be collected immediately prior to the study vaccination for baseline serology and cytokine assays.
- Subjects will be enrolled in Advantage eClinical and assigned to treatment arm (BOOSTRIX or Td) and post-partum study schedule.

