##### **3.1.3. Exploratory**

###### **Immunogenicity:**

- To assess the effects of maternal age, parity, gestational age (GA) at which the vaccine is given, GA at delivery, and infant birthweight on antibody responses to BOOSTRIX in pregnant women at time of delivery, and in their newborn infants at birth.
- To assess maternal secretory immunity through measurement of breast milk antibodies to Tdap vaccine antigens in women at the time of delivery, at 6 weeks postpartum, at 10 weeks (in ½ of women) or 18 weeks (in ½ of women) postpartum, and at 6 months after delivery.
- To assess the cytokine profile after stimulation in vitro with diphtheria, tetanus and pertussis antigens of peripheral blood mononuclear cells (PBMC) obtained from women before and one month after receiving Tdap or Td.

- To assess the cytokine profile after stimulation in vitro with diphtheria, tetanus, and pertussis antigens of PBMC obtained from infants before the first dose of DTwP (approximately 6 weeks of age) in all subjects, one month after the first dose of DTwP (approximately 10 weeks of age) in ½ of infants, one month after the last dose of DTwP (approximately 18 weeks of age) in ½ of infants, and at 6 months of age in all infants.

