	One month after receipt of last dose of DTwP (approximately 18 weeks of age)	n			
		GMC (95% CI)			
		Median (Q1, Q3)			
		Min, Max			
	Change from prior to first to post last dose of DTwP	n			
		Median (Q1, Q3)			
		Min, Max			
	6 months of age	n			
		GMC (95% CI)			
		Median (Q1, Q3)			
		Min, Max			
	Change from prior to first dose of DTwP to 6 months of age	n			
		Median (Q1, Q3)			

Table 35: Multiplex Assays Stimulated Peripheral Blood Cells Results with 95% Confidence Intervals by Cytokine, Time Point, and Treatment Group -- Infant Intent-to-Treat Population (continued)

Cytokine	Time Point	Statistic	BOOSTRIX (N=X)	Td (N=X)	Difference
		Min, Max			

Note: N=Number of subjects in the Infant ITT Population  
n=Number of subjects with results available at time point

Table with similar format:

**Table 36: Multiplex Assays Stimulated Peripheral Blood Cells Results with 95% Confidence Intervals by Cytokine, Time Point, and Treatment Group -- Infant Per Protocol Population**

**Table 37: Serum IgG Anti-PT ELISA GMC Results with 95% Confidence Intervals at Delivery Stratified by Maternal Cofactors -- Maternal Intent-to-Treat Population**

Cofactor	n	GMC	95% CI
Maternal Age			
18-29 years old	x	x.x	(x.x, x.x)
30-39 years old			
Parity			
Primiparous			
Multiparous			
GA at Time of Vaccination			
14-17 weeks			
18-21 weeks			
22-26 weeks			
GA at Time of Delivery			
28-32 weeks			
33-36 weeks			
37 or more weeks			

Tables with similar format:

**Table 38: Serum IgG Anti-PT ELISA GMC Results with 95% Confidence Intervals at Delivery Stratified by Maternal Cofactors -- Maternal Per Protocol Population****Table 39: Serum IgG Anti-PT ELISA GMC Results with 95% Confidence Intervals at Birth Stratified by Maternal Cofactors -- Infant Intent-to-Treat Population****Table 40: Serum IgG Anti -PT ELISA GMC Results with 95% Confidence Intervals at Birth Stratified by Maternal Cofactors -- Infant Per Protocol Population**

**Table 41: Regression Analysis to Evaluate the Relationship of Anti-PT ELISA Response and Maternal Cofactors at Delivery -- Maternal Intent-to-Treat Population, BOOSTRIX**

Model Parameter	n	Parameter Estimate	SE	p-value	Ratio*	95% CI of Ratio
Maternal Age						
Intercept	x	xxx.x	xxx.x	0.xxx	NA	NA
18-29 years old (reference)	x	NA	NA	NA	NA	NA
30-39 years old	x	xxx.x	xxx.x	0.xxx	xxx.x	(xxx.x, xxx.x)
Parity						
Intercept						

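### The SAP 8.3.1 cofactor models describe PT level at delivery or birth; without a Day 1 PT term they cannot separate prior antibody from the response to BOOSTRIX, which the objective asks about

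*SAP*

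**What the plan says.** The exploratory objective in SAP 3.1.3 (Protocol 3.1.3 has the same text) concerns the effects of maternal age, parity, gestational age at vaccination and at delivery, and birthweight "on antibody responses to BOOSTRIX in pregnant women at time of delivery, and in their newborn infants at birth". The matching endpoint in SAP 3.2.3 is worded differently: it asks about independent associations of these cofactors with the PT GMC.

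SAP 8.3.1 sets out the analysis.

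- Results are "presented for maternal and infant subjects in the BOOSTRIX group for anti-PT antibody responses at time of delivery or birth, as applicable".
- The models are introduced thus: "Additionally, regression modelling will be employed to evaluate the association of log-transformed anti-PT antibody response with each of the stratified maternal cofactors defined previously".
- The outcome is the log PT titer. The right-hand side holds an intercept, one cofactor and error, and nothing else.
- "Separate models will be used for each analysis population and each cofactor".
- For categorical cofactors, "the ratio of the GMC of each non-reference level with respect to the GMCs of the reference level will be computed", with a 95% confidence interval. The shells for Tables 41 to 44 add p-values. Table 41 is titled "Regression Analysis to Evaluate the Relationship of Anti-PT ELISA Response and Maternal Cofactors at Delivery -- Maternal Intent-to-Treat Population, BOOSTRIX".

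Pre-vaccination blood exists. Protocol 7.3 states that about 30 mL of "venous blood will be collected immediately prior to the study vaccination for baseline serology and cytokine assays". SAP 6.3.2 drops from the maternal per-protocol set any woman without baseline results. Yet maternal antibody time points in SAP 4.5.2, SAP 8.2.1 and Table 25 begin one month after vaccination, and no antibody model or table uses the Day 1 value. The maternal cytokine analysis in SAP 8.3.3, by contrast, reports the pre-vaccination value and the change from it. Neither SAP 6.4 nor Protocol 11.4.3 adds a baseline term.

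**The concern.** PT antibody at delivery is the sum of what the woman already had and what the vaccine induced. The cofactors are not randomised and the Td arm is left out, so the model cannot tell the two apart. Fitting the cofactors jointly would not do so either.

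Prior antibody is foreseeable. Protocol 2.1.4 discusses antibody already present in unvaccinated pregnant women, and earlier pertussis vaccination or infection is not an exclusion in Protocol 5.2. Age and parity could plausibly relate to earlier exposure. The case is weaker for gestational age and birthweight.

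A reader who takes the ratios in Tables 41 to 44 as answers to the objective could therefore credit a cofactor with a difference in vaccine response that reflects Day 1 antibody. The reader could also miss a weaker response in a group that started higher.

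**Working it through.** **Reproducing the plan's figure.** The documents give no power or precision for the cofactor models. The nearest figure is maternal PT at delivery in Protocol Table 10 (SAP Table 4): GMC 51, log SD 0.90, N=133. The interval is GMC × exp(± t × SD/√n). This gives 43.7 to 59.5, as stated. The SD of 0.90 is used below.

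**Inputs.** From the documents: n=133 in the BOOSTRIX arm, about 113 after the 15% loss in SAP 5, and log SD 0.90. The two-sided 0.05 level is stated only for the arm comparison and is borrowed here. Assumed, because the documents give none of them: the Day 1 difference between cofactor groups, the correlation between Day 1 and delivery log titers, and the share of women in the group.

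**Central illustration.** Suppose the cofactor has no effect on the delivery level once Day 1 PT is known. Take a Day 1 difference of 0.5 SD, correlation 0.5 and 25% in the group.

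- Expected shift in log titer: 0.90 × 0.5 × 0.5 = 0.225; ratio exp(0.225) = 1.25.
- Standard error with 33 and 100 women: 0.90 × √(1/33 + 1/100) = 0.181.
- 0.225/0.181 = 1.24, so by normal approximation p<0.05 occurs about 24% of the time. Simulation (4,000 trials) gives 23.2%, and 5.2% with the Day 1 titer in the model.
- At n=113: 20.4% and 5.0%.
- For infants, with SD 0.78 from the same table: 23.7% and 4.7%; ratio exp(0.78 × 0.25) = 1.22.

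Over Day 1 differences of 0.25 to 0.75 SD, correlations of 0.3 to 0.7 and shares of 25% to 40%, the crude rate runs from 6% to 83%. The adjusted rate is 4% to 6%.

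**Second parameterisation.** Let Day 1 GMC differ r-fold between groups and let delivery log titer rise by b per unit of Day 1 log titer. With no effect given baseline, the crude ratio is r^b. The baseline log SD is assumed to be 1.0, with 20,000 runs per row. The last two columns give the share of runs with p<0.05 in the planned model.

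| r | b | Crude ratio | n=133, 50:50 split | n=113, 30:70 split |
|---|---|---|---|---|
| 1.5 | 0.25 | 1.11 | 10% | 9% |
| 1.5 | 0.5 | 1.22 | 26% | 20% |
| 1.5 | 0.75 | 1.36 | 49% | 37% |
| 2 | 0.25 | 1.19 | 20% | 15% |
| 2 | 0.5 | 1.41 | 60% | 46% |
| 2 | 0.75 | 1.68 | 91% | 80% |

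With r=1, meaning no link to Day 1 PT, the planned model stays at about 5%. With ln(Day 1 PT) added, the ratio returns to 1.00 and the rate to between 4.6% and 5.3% in every scenario.

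**The opposite direction.** In the central illustration, let the group truly respond 0.45 log units lower given baseline. The crude shift is −0.45 + 0.225 = −0.225. Power is 23% crude and 78% with Day 1 titer. The value 0.45 is a choice, twice the assumed baseline contribution, so half the effect cancels.

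**The case against.** The strongest reply is that the planned model does what its endpoint asks. SAP 3.2.3 and 8.3.1 speak of association, and the Table 41 footnote defines the ratio as one group's GMC over the reference group's. The documents also use response loosely for a post-vaccination level; the title of Table 10 is an example. This stands. A reader might infer that the ratio of 1.25 above is spurious. It is not: under those assumptions PT GMC really does differ by that factor, and the crude model estimates it without bias. The level itself matters, since Protocol 2.1.4 stresses anti-PT antibody in the infant's first months.

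Nor is Day 1 adjustment simply the removal of confounding. If age or parity acts through earlier antibody, Day 1 titer lies on the pathway, and conditioning on it answers a different question. This also stands.

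Third, the analysis is exploratory, SAP 6.4 disclaims power for subgroups, SAP 6.8 says no specific null hypothesis is tested, and the link to Day 1 PT is assumed throughout. All true; this limits the weight of the point. It does not remove the gap between an objective worded as effects on response to BOOSTRIX and a model of level.

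A reader might also suppose that the ratios are meant to settle when to vaccinate. No section gives them that purpose, and gestational age at vaccination is not among the cofactors most plausibly tied to Day 1 PT.

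**Conclusion.** The cofactor models fit their endpoint but only partly serve their objective. They show which cofactors go with PT level at delivery or birth in BOOSTRIX dyads; they cannot show whether the response to the vaccine differs.

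The gap matters only for a cofactor linked to Day 1 PT. Its size is unknown, because the documents give neither the Day 1 difference nor the correlation. The simulated range, from near nominal to above 80%, shows what is possible and does not estimate the trial's error rate. The planned model is not in error as a description of level, and an adjusted ratio would not be a causal effect of the cofactor on response. This is a cheap improvement of low severity.

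**What to change.** In SAP 8.3.1 and Tables 41 to 44:

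- Keep the planned model and label its ratio as the association with PT level.
- Beside it, at least for maternal age and parity, add ln(titer) = b0 + b1·x + g·ln(maternal Day 1 anti-PT), for both the maternal and the infant outcome. Label its ratio as the association with PT level given pre-vaccination antibody, and state that it is not a causal effect.

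The cost is one covariate and extra columns in four tables. No new visit or sample is needed: Day 1 blood is already drawn, and the maternal per-protocol definition already expects baseline results. The SAP should confirm that the PT ELISA is run on that sample, since its list of maternal antibody time points omits Day 1. Protocol 11.4.3 specifies only regression modelling, so the addition fits within it. The downside is that dyads without a Day 1 result drop out of the adjusted column, so n should be shown for each model.

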11.4.3. Immunogenicity Data (ELISA)

Immunogenicity data summaries and analysis for pregnant women will be presented for the ITT and the PP populations. Immunogenicity data summaries and analysis for infants will be presented for the infant ITT and infant PP populations.

Immune responses will be reported for antibodies against each of the antigens in the vaccine and at each time point for each subject group- pregnant women receiving BOOSTRIX, pregnant women receiving Td, and the infants of women who received BOOSTRIX or Td while pregnant. GMC and corresponding 95% confidence intervals will be reported.

For each antigen, GMC will be compared between treatment arms using a t-test on log-transformed ELISA titers.

The level of antibody transplacentally transferred will be summarized as the Geometric Mean Ratio (GMR), with corresponding 95% confidence interval, of mother's concentration to infant's concentration for all mother-infant pairs for which both the mother and infant have data at the applicable time point (delivery/birth).

Graphical presentations of immune response may include reverse cumulative distribution (RCD) curves, and longitudinal presentations of GMTs.

To evaluate the association with of maternal immunogenicity cofactors, Maternal and Infant anti-PT ELISA response will be summarized stratified by maternal age (18-29, 30-39 years old), parity (primiparous vs. multiparous), GA at time of vaccination (14-17, 18-21, 22-26 weeks), GA at time of delivery (28-32, 33-36, 37 or more weeks), and infant birthweight, and these cofactors will be evaluated in regression modeling.

Antibody responses in breast milk/colostrum will be evaluated in a similar way to above.

Additional exploratory analyses, including analysis of cytokine response will be described in the statistical analysis plan.

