### 3.2.3. Exploratory

#### Immunogenicity:

- Maternal immunogenicity cofactors for maternal and neonatal anti-PT antibody responses following intrapartum BOOSTRIX: Maternal age (18-29, 30-39 years old), parity (primiparous vs. multiparous), GA at time of vaccination (14-17, 18-21, 22-26 weeks), GA at time of delivery (28-32, 33-36, 37 or more weeks), and infant birthweight as potential independent associations with PT GMC.
- Maternal secretory immunity: GMC of breast milk IgG and Immunoglobulin A (IgA) antibodies to Tdap vaccine antigens (PT, FHA, PRN, tetanus, diphtheria) as measured by ELISA in women at the time of delivery, at 6 weeks after delivery, at 10 weeks (in ½ of women) or 18 weeks (in ½ of women) after delivery, and 6 months after delivery after intrapartum receipt of BOOSTRIX versus Td.
- Maternal cytokine responses: Cytokines produced by peripheral blood cells stimulated with DTwP vaccine antigens, as measured by multiplex assays, in women before and one month after receiving Tdap or Td. Cytokines measured will include: Interferon (IFN)- $\gamma$ , Inerleukin (IL)-10, IL-12p70, IL-12/IL-23p40, IL-13, IL-15, IL-16, IL-17A, IL-1 $\alpha$ , IL-1 $\beta$ , IL-2, IL-4, IL-5, IL-6, IL-7, IL-8, Tumor Necrosis Factor (TNF)- $\alpha$ , and TNF- $\beta$ .
- Infant cytokine responses: Cytokines produced by infant peripheral blood cells stimulated with DTwP antigens from infants whose mothers received intrapartum BOOSTRIX versus Td, measured by multiplex assays before the first dose (or umbilical cord blood), one month after the first dose of DTwP (~10 weeks of age, ½ of subjects), one month after the last dose of study vaccine (approximately 18 weeks, ½ of subjects), and at 6 months of age. Cytokines measured will include: IFN- $\gamma$ , IL-10, IL-12p70, IL-12/IL-23p40, IL-13, IL-15, IL-16, IL-17A, IL-1 $\alpha$ , IL-1 $\beta$ , IL-2, IL-4, IL-5, IL-6, IL-7, IL-8, TNF- $\alpha$ , and TNF- $\beta$ .

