## 5. SAMPLE SIZE CONSIDERATIONS

Based on the accrual rate for similar studies, it seems reasonable to expect that the sites will be able to enroll this study in a timely fashion. Prior experience suggests up to 15% of subjects may be excluded from the per protocol analysis for the primary immunogenicity outcome either because they were lost-to-follow-up or otherwise do not have data available following the study vaccination, or because they had a protocol deviation requiring their exclusion from the per protocol analysis.

The study is planned to enroll 200 pregnant women (133 BOOSTRIX, 67 Td) and their infants.

This will be one of the first studies of maternal Tdap vaccination in an African, low resource setting, and where infants received whole cell, rather than acellular pertussis vaccinations. Thus, this study is intended to obtain preliminary estimates of immune response in this setting; it is not designed to test a specific null hypothesis.

**Table 3** indicates the probability of observing one or more safety event, such as solicited injection site or systemic symptom, or an unsolicited adverse event of a particular type within a treatment arm.

In addition to safety, as a co-primary objective, the study will assess serum PT antibody at birth among infants whose mothers received a single dose of BOOSTRIX or Td, and as secondary and exploratory objectives, the study will assess maternal and infant humoral response to all vaccine antigens. Immune response will be measured by ELISA. **Table 4** presents the precision (95% confidence interval (CI)) available for estimating GMC of ELISA titers against the vaccine component using assumptions for GMC and standard deviation (SD) for maternal and infant response to Tdap from Munoz et al. [10] and infant response post third dose of primary DTwP vaccine series from Ladhani et al. [11]

**Table 5** presents the minimum difference in infant PT antibody GMC at birth between the Td and Tdap (BOOSTRIX) vaccination arms that would be detectable with 80% power. The assumed GMC and SD used for these calculations are based on the PT antibody GMC and SD observed at birth in infants whose mother received either Tdap or placebo vaccination during pregnancy, reported in Munoz et al. [10] The calculations are based on a two-sided two sample T-test to compare means, with alpha = 0.05.

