## **6.4. Covariates and Subgroups**

This study is not powered for formal subgroup analyses; however, immunogenicity subgroups will be explored.

To evaluate the association with maternal immunogenicity cofactors, maternal and infant anti-PT ELISA response will be summarized stratified by maternal age (18-29, 30-39 years old), parity (primiparous vs. multiparous), GA at time of vaccination (14-17, 18-21, 22-26 weeks), GA at time of delivery (28-32, 33-36, 37 or more weeks), and infant birthweight. These cofactors will be evaluated in regression modeling.

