Primiparous (reference)						
Multiparous						
GA at Time of Vaccination						
Intercept						
14-17 weeks (reference)						
18-21 weeks						
22-26 weeks						
GA at Time of Delivery						
Intercept						
28-32 weeks (reference)						
33-36 weeks						
37 or more weeks						
Infant Birthweight (kg)						
Intercept	x	xxx.x	xxx.x	0.xxx	NA	NA
Infant Birthweight	n	xxx.x	xxx.x	0.xxx	NA	NA

\*The ratio is the anti-PT antibody GMC of the relevant group divided by the GMC of the reference group.

Tables with similar format:

**Table 42: Regression Analysis to Evaluate the Relationship of Anti-PT ELISA Response and Maternal Cofactors at Delivery -- Maternal Per Protocol Population, BOOSTRIX**

**Table 43: Regression Analysis to Evaluate the Relationship of Anti-PT ELISA Response and Maternal Cofactors at Birth -- Infant Intent-to-Treat Population, BOOSTRIX**

**Table 44: Regression Analysis to Evaluate the Relationship of Anti-PT ELISA Response and Maternal Cofactors at Birth -- Infant Per Protocol Population, BOOSTRIX**

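### The exploratory cofactor endpoint asks for independent associations with PT GMC, but the SAP fits only one-cofactor models, which give crude associations

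*SAP*

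**What the plan says.** The endpoint is worded the same way in Protocol 3.2.3 and SAP 3.2.3. It lists maternal age, parity, GA at vaccination and GA at delivery, and ends with "infant birthweight as potential independent associations with PT GMC".

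The protocol's analysis text (11.4.3) leaves the form of the model open, saying only "and these cofactors will be evaluated in regression modeling". SAP 6.4 says the same.

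SAP 8.3.1 settles it, for the BOOSTRIX group: "Separate models will be used for each analysis population and each cofactor". It writes out two equations. One regresses ln(titer) on the levels of a single categorical cofactor; the other regresses ln(titer) on birthweight alone.

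The shell for Table 41, which is also the format for Tables 42 to 44, matches this. It has a separate intercept for every cofactor, a p-value for each parameter, and a footnote defining the result as a crude ratio: "The ratio is the anti-PT antibody GMC of the relevant group divided by the GMC of the reference group". Neither document contains a model that adjusts the cofactors for one another.

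**The concern.** An independent association is what remains of a factor's relation to the outcome once the other factors are held fixed. A one-cofactor model estimates that only if the cofactors are uncorrelated or the omitted ones have no effect. The documents claim neither. It is also unlikely that age is unrelated to parity, or birthweight to GA at delivery.

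The risk is that birthweight is reported as a determinant of infant PT antibody when it partly stands in for GA at delivery, or age when it partly stands in for parity. Tables 41 to 44 print a p-value for each cofactor and nothing that would expose a proxy. These are hypothesis-generating results that later maternal vaccination studies may use.

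**Working it through.** The documents attach no sample size, power or alpha to this analysis, so there is no stated figure to reproduce. The mismatch is established by the texts above. What follows shows how large the distortion could be.

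**Inputs from the documents**
- BOOSTRIX arm: 133 planned (SAP 5).
- Loss from the per-protocol analysis: up to 15% (SAP 5), so 133 × 0.85 = 113.
- Log-scale SD of infant PT at birth after maternal Tdap: 0.78 (SAP Table 4).

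**Assumed, because the documents give no value**
- Correlation *r* of birthweight with GA at delivery.
- Correlation *b* of GA at delivery with ln(PT).
- Birthweight has no effect of its own.
- Two-sided 5% test.

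**Birthweight standing in for GA at delivery.** The crude correlation of birthweight with ln(PT) is then *r* × *b*. By the Fisher transformation, the chance of significance is approximately Φ(atanh(*rb*) × √(113 − 3) − 1.96), plus a negligible or small opposite tail.

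| *r* | *b* | *rb* | atanh(*rb*) × √110 | P(p < 0.05) |
|---|---|---|---|---|
| 0.3 | 0.3 | 0.09 | 0.95 | 0.16 |
| 0.5 | 0.3 | 0.15 | 1.59 | 0.35 |
| 0.7 | 0.4 | 0.28 | 3.02 | 0.85 |

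The correct value is 0.05 in every row.

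**Age standing in for parity.** Assume that age has no effect, that the multiparous-to-primiparous GMC ratio is R, and that the multiparous share differs by *d* between the two age groups. The false age ratio is exp(*d* × ln R).
- R = 0.7, *d* = 0.20 (90% v 70%): exp(0.20 × −0.357) = 0.93.
- R = 0.6, *d* = 0.35 (95% v 60%): exp(0.35 × −0.511) = 0.84.
- R = 0.8, *d* = 0.05: exp(0.05 × −0.223) = 0.99.

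The first two cases were simulated with 133 women, 30% of them aged 30 to 39, and SD 0.78. The one-cofactor model called age significant in 7% and 20% of runs. With parity in the model, the age ratio returned to 1.00 with about 5% false positives.

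**Does any adjustment work?** The SAP groups GA at delivery as 28–32, 33–36 and 37 or more weeks, with 28–32 weeks as the reference. Simulations used 113 infants, the two stronger rows of the birthweight table, and an assumed 6 to 10% of births before 37 weeks, with 1 to 1.5% before 33.
- Adjusting for the bands still left birthweight falsely significant in about 18 to 68% of runs.
- Adjusting for continuous GA brought this to about 5%.
- The reference band would hold about 113 × 0.01 = 1.1 to 113 × 0.015 = 1.7 infants. It would be empty with probability 0.985^113 = 0.18 to 0.99^113 = 0.32.

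**Can the model be fitted?** Age, parity and GA at vaccination need 1 + 1 + 2 = 4 slopes. Adding continuous GA at delivery and birthweight makes 6. With 113 subjects that is about 28 and 19 per slope.

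**The case against.** The conflict rests on one adjective in an exploratory endpoint. The matching objective speaks only of assessing effects, SAP 8.3.1 describes its aim as evaluating association, and SAP 6.4 says the study is not powered for formal subgroup analyses. All of this is true. A reader might infer that the protocol promised a multivariable model and the SAP withdrew it. The documents do not support that, since the protocol's analysis section leaves the form of regression open. Rewording the endpoint to unadjusted associations would also remove the mismatch, but it would give up the question the endpoint asks.

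The size of the problem is assumed. Weak correlations give a false-positive rate not far above nominal, as the 7% age case shows. This stands, and it is why a range is given.

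A single model with all five cofactors would bring its own problems. GA at delivery and birthweight arise after vaccination and may lie on the path from age or parity to antibody level, so adjusting for them changes the question asked about the earlier factors. The banded GA variable would also leave much of the confounding in place and rest on a nearly empty reference level. Both points stand, and they shape the remedy. They do not make the one-cofactor models answer the endpoint.

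**Conclusion.** The point holds as a mismatch between an exploratory endpoint and its model: the planned models estimate crude associations and cannot show independence. That follows from the texts and needs no assumption beyond some correlation among cofactors that matter.

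Its size cannot be computed from the documents. With 113 infants and no true birthweight effect, the false-positive rate is about 16% if both correlations are 0.3. It is about 35 to 85% if birthweight correlates 0.5 to 0.7 with GA at delivery and GA at delivery 0.3 to 0.4 with ln(PT).

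Two stronger readings are not supported. A reader might take the upper figures as a forecast, but they rest on correlations the documents do not supply, and only a fraction of the correlated factor's effect (*rb*, not *b*) passes through. A reader might also doubt the main results, but no primary or secondary analysis uses these models.

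**What to change.** In SAP 8.3.1, keep the one-cofactor models and label them unadjusted. Add, for each analysis population in the BOOSTRIX arm, a staged adjusted model of ln(PT):

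1. Maternal age, parity and GA at vaccination.
2. The same terms plus GA at delivery as a continuous variable (Table 18 already summarizes it in days) and birthweight.

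Add the adjusted GMC ratios with 95% CIs to Tables 41 to 44, per stated unit for the continuous terms. State that any claim of independent association rests on the adjusted models.

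No new data, visits or subjects are needed. The cost is a little more analysis and wider intervals for GA at delivery and birthweight, because the two are correlated. The change should be made before database lock, so that the adjustment set is not chosen after the results are seen.
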